Detailed Description: The clinical relevance of this proposed screen is that it would lead to the elusive and accurate diagnosis to circumvent the inexact IC patients into authentic CC and UC with a first clinic endoscopy biopsy. The central medical challenge in endoscopic medicine and colorectal surgery is the discrimination of colonic IBD into the subtypes with high accuracy because it greatly affects surgical care of patients. Incorrect diagnosis and surgery carry potential morbidity from inappropriate and unnecessary surgery and cost. Our published data has shown robust evidence supporting presence of human alpha-defensin 5 (DEFA5) in areas of the colon mucosa with aberrant expression of apparent Paneth cell-like cells (PCLCs) / crypt cell-like cells (CCLCs), which identifies an area of colonic ileal metaplasia, consistent with the diagnosis of CC. Investigators propose to demonstrate that UC and CC, the two unsolved medical subtypes of GI pathology with no drugs for a cure, may accurately be distinguished molecularly by examining CCLCs-secreted DEFA5 in colonic endoscopy biopsies instantly. Our proposal is highly innovative, as it highlights the robustness efficacy and safety of DEFA5 and its clinical relevance in IBD diagnostics. The goal of this proposal is to develop a clinical approach to circumvent diagnostic ambiguity and delay, as well as permit timely and accurate diagnosis of colonic IBD. DEFA5 immunoreactivity in colonic endoscopy biopsies could be a potential diagnostic signature that accurately diagnoses CC and provides the basis to resolve ambiguity in the diagnosis of IBD to not only circumvent diagnostic delay, but also permit timely, accurate diagnosis and timely prescription of appropriate treatment options, an Affordable, Sensitive, Specific, User-friendly, Robust and Rapid, Equipment-free, and Deliverable (ASSURED) bioassay that may delineate subtypes of IBD during the first clinic endoscopy biopsy visit. This bioassay is specific, sensitive, linear, affordable, low risk, and less invasive. Investigators hypothesize that aberrant expression of DEFA5 secreting CCLCs in colonic crypt of IBD patients may be exploited as a reliable diagnostic signature to highly differentiate CC from UC in otherwise IC patients during the first clinic visit endoscopy biopsy without delay. Investigators foresee no issues pertaining

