to this proposal as an established sampling error by endoscopic biopsy making it does not interfere with results and apropos of this project that each biopsy has complement CCLCs with co-localized DEFA5 clearly restricted in areas of the mucosa with aberrant CCLCs identifies a ubiquitously colonic ileal metaplasia that is consistent with the diagnosis of authentic CC. If successful, widespread use of this approach would not only revolutionize provide accurate diagnoses and the correct treatment regimens for IBD patients, but also it will improve health outcomes and patient quality of life, while reducing medical complications and/or unnecessary drugs, surgeries, & costs.

Conditions

Conditions: Inflammatory Bowel Diseases
 Ulcerative Colitis
 Crohn's Colitis
 Indeterminate Colitis

Keywords: Inflammatory bowel disease
 Crohn's colitis
 Ulcerative colitis
 Indeterminate colitis
 DEFA5
 Molecular diagnostics
 Colonic biopsies
 Colonic ileal metaplasia

Study Design

Study Type: Observational
 Observational Study Model: Cohort

Time Perspective: Cross-Sectional

Biospecimen Retention: Samples With DNA

Biospecimen Description: The research outlined is consistent with the Non-human Welfare Act Criteria because investigators receive de-identified specimens and data from an IRB approved repository, and investigators do not have access to the link by which investigators may re-identify the specimens and data with their source. The research involves the use of human tissue acquired previously using the third-party good faith broker mechanism. Since all identifiers are striped, the tissue samples are considered non-human subjects. Each specimen is assigned a unique barcode identifier to maintain the patient's confidentiality. In no case is the patient's name ever revealed to the users. All information accompanying the specimen(s) uses the bar code identifier.

Enrollment: 230 [Anticipated]

Number of Groups/Cohorts: 5

Groups and Interventions

Groups/Cohorts	Interventions
Crohn's colitis Correlate patient longitudinal study of clinical data and their biopsy data. Investigators will determine DEFA5 levels from endoscopy biopsies from known authentic CC patients.	Diagnostic Test: Diagnostic Test The challenge is the discrimination of IBD into the subtypes with accuracy because it affects surgical care of patients. Investigators have developed a signature discriminator between UC&CC that also predicts the outcome of IC patients into

Groups/Cohorts	Interventions

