	
authentic UC/CC. This is a bioassay that is specific, sensitive, linear, affordable, minimal risk, non-invasive and constitutes an inexpensive, simple to use, point-of-care test format. Our published data have shown robust evidence supporting presence of DEFA5 in the colon crypt mucosa with aberrant expression of apparent crypt-cell-like cells (CCLCs) in areas identified with ectopic colon ileal metaplasia consistent with CC. Investigators propose to validate that UC/CC, the two unsolved medical sub-types of pathology can accurately be distinguished among IC patients by examining CCLCs secreted DEFA5 levels in endoscopy biopsies instantly. Diagnostics relies on the expression/localization/activation of DEFA5 and the ectopic CCLCs in the mucosal crypt of CC patients.

Ulcerative colitis Correlate patient longitudinal study of clinical data and their biopsy data. Investigators will determine DEFA5 levels from endoscopy biopsies from known authentic UC patients.
	
Diagnostic Test: Diagnostic Test The challenge is the discrimination of IBD into the subtypes with accuracy because it affects surgical care of patients. Investigators have developed a signature discriminator between UC&CC that also predicts the outcome of IC patients into authentic UC/CC. This is a bioassay that is specific, sensitive, linear, affordable, minimal risk, non-invasive and constitutes an inexpensive, simple to use, point-of-care test format. Our published data have shown robust evidence supporting presence of DEFA5 in the colon crypt mucosa with aberrant expression of apparent crypt-cell-like cells (CCLCs) in areas identified with ectopic colon ileal metaplasia consistent with CC. Investigators propose to validate that UC/CC, the two unsolved medical sub-types of pathology can accurately be distinguished among IC patients by examining CCLCs secreted DEFA5 levels in endoscopy biopsies instantly. Diagnostics relies on the expression/localization/activation of DEFA5 and the ectopic CCLCs in the mucosal crypt of CC patients.

Indeterminate colitis Correlate patient longitudinal study of clinical data and their biopsy data. Investigators will determine DEFA5 levels from endoscopy biopsies from
	
Diagnostic Test: Diagnostic Test The challenge is the discrimination of IBD into the subtypes with accuracy

Groups/Cohorts	Interventions

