Ileum Positive control	Diagnostic Test: Diagnostic Test The challenge is the discrimination of IBD into the subtypes with accuracy because it affects surgical care of patients. Investigators have developed a signature discriminator between UC&CC that also predicts the outcome of IC patients into authentic UC/CC. This is a bioassay that is specific, sensitive, linear, affordable, minimal risk, non-invasive and constitutes an inexpensive, simple to use, point-of-care test format. Our published data have shown robust evidence supporting presence of DEFA5 in the colon crypt mucosa with aberrant expression of apparent crypt-cell-like cells (CCLCs) in areas identified with ectopic colon ileal metaplasia consistent with CC. Investigators propose to validate that UC/CC, the two unsolved medical sub-types of pathology can accurately be distinguished among IC patients by examining CCLCs secreted DEFA5 levels in endoscopy biopsies instantly. Diagnostics relies on the expression/localization/activation of DEFA5 and the ectopic CCLCs in the mucosal crypt of CC patients.

Outcome Measures

Primary Outcome Measure:

1. Assesse investigator's two newly developed anti-DEFA5 monoclonal antibodies for immunohistochemistry and sandwich ELISAs, and determines the most effective one or both for bioassay kit for IBD diagnostics.
 [Time Frame: Six months]

Secondary Outcome Measure:

2. Assess expression of DEFA5 biomarker in colonic biopsies from known patients with the diagnosis of IBD i.e., UC, CC, IC, and none-IBD i.e., diverticulitis, diverticulosis, & ileum as positive control, this will differentiate UC vs. CC and IC into authentic UC and CC.
 [Time Frame: 12 months]

Eligibility

Study Population: A sample size of 230 subjects is sufficient to detect a clinically significant difference of 19% between the PPVs of CC and UC using a one-tailed test of proportions between the two groups with 80% statistical power and a 5% level of significance. This 19% difference represents 80% probability that subjects in the CC group with a positive screening test truly have the disease and 77% PPV for subjects in UC group. Investigators will add non-IBD samples, 46 in the DV arm and 46 in CP arm to strengthen the results.

Sampling Method: Probability Sample

Minimum Age:

Maximum Age:

Sex: All

Gender Based: No

Accepts Healthy Volunteers: Yes

Criteria: Inclusion Criteria:

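### The 230 is justified by a difference between the PPVs of CC and UC, a contrast that does not measure whether DEFA5 separates the two diseases

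*Protocol*

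**What the plan says.** The Study Population entry under Eligibility says that 230 subjects suffice to detect a 19% difference between the "PPVs of CC and UC using a one-tailed test of proportions between the two groups", with 80% power at the 5% level. It explains the difference as "80% probability that subjects in the CC group with a positive screening test truly have the disease", set against a PPV of 77% in the UC group. The only arm sizes it gives are for non-IBD specimens: "46 in the DV arm and 46 in CP arm to strengthen the results".

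The stated purpose is discrimination. The secondary outcome is DEFA5 expression in biopsies, of which the Protocol says "this will differentiate UC vs. CC and IC into authentic UC and CC". The hypothesis in the Detailed Description is that DEFA5 expression can serve as "a reliable diagnostic signature to highly differentiate CC from UC in otherwise IC patients".

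Groups and Interventions fixes the diagnosis before the assay is run: "Investigators will determine DEFA5 levels from endoscopy biopsies from known authentic CC patients", and likewise "Investigators will determine DEFA5 levels from endoscopy biopsies from known authentic UC patients".

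No other hypothesis test is stated. The logistic model in the Brief Summary is earlier work on colectomy specimens, and the hypothesis in the Detailed Description names no test.

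**The concern.** A good assay makes both predictive values high: a CC call is usually right and so is a UC call. The better the assay, the closer both values come to 100% and the smaller their difference. A test for a difference between them therefore looks for something that a good assay need not show and that a poor one can show. If so, the 230 carries no information about how well the study can establish CC/UC separation, although that is the purpose the Protocol gives for the biopsy work.

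**Working it through.** **Inputs.** From the Protocol: total 230, five groups, a 19-point difference, PPVs of 80% and 77%, one-tailed 5% level, 80% power, two non-IBD arms of 46. Assumed, because not stated: PPV(CC) = TP/(TP+FP) and PPV(UC) = TN/(TN+FN), where a positive result is a CC call; the tail PPV(CC) > PPV(UC), suggested by the order of the printed figures; and 46 per arm (230/5 = 46, matching the two stated arms), with 115 per arm (230/2) as the upper end.

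**1. The plan's own figure.** The usual formula for two proportions is n per group = [1.645·√(2p̄(1−p̄)) + 0.842·√(p₁(1−p₁)+p₂(1−p₂))]² / (p₁−p₂)².
- 80% against 77% is 3 points, not 19. It needs 2,318 per group; 115 per group gives 14% power and 46 gives 10%.
- 96% against 77% is 19 points, taking 96% from the PPV in the Brief Summary; that link is inferred. It needs 39 per group, 78 in total.
- 80% against 61% needs 71 per group, 142 in total.

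None of these gives 230. The mismatch is a separate error and the point below does not depend on it.

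**2. What the PPV difference depends on.** Let π be the CC share of the CC and UC specimens, Se the sensitivity for CC and Sp the specificity in UC.
- Odds of PPV(CC) = πSe / [(1−π)(1−Sp)]
- Odds of PPV(UC) = (1−π)Sp / [π(1−Se)]

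Hence PPV(CC) > PPV(UC) if and only if π²Se(1−Se) > (1−π)²Sp(1−Sp). With equal arms this reduces to Se(1−Se) > Sp(1−Sp), which compares the two error patterns and not the accuracy. For a perfect assay both sides are zero at any mix.
- 95%/95%, equal arms: both PPVs are 95%, difference 0.
- 60%/95%, equal arms: 0.60/0.65 = 92.3% against 0.95/1.35 = 70.4%, difference 21.9 points.

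**3. How often the test rejects, equal arms.** Exact enumeration of TP ~ Bin(n, Se) and TN ~ Bin(n, Sp), pooled z, reject if z > 1.645, undefined z counted as no rejection:

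| Se/Sp | 46:46 | 115:115 |
|---|---|---|
| 100%/100% | 0% | 0% |
| 95%/95% | 4% | 3% |
| 90%/90% | 2% | 2% |
| 60%/95% | 93% | 100% |
| 90%/99% | 63% | 93% |
| 99%/90% | 0% | 0% |

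The last two rows are mirror images with the same overall accuracy. With the opposite tail the pairs swap: 95%/60% rejects 93% (100%) and 60%/95% 0% (0%).

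**4. Unequal arms (hypothetical).** For a marker with no discrimination (50%/50%), PPV(CC) = π and PPV(UC) = 1−π, so the difference is 2π−1. That is exactly 19 points at π = 59.5%.
- 92 specimens: rejects about 0% at 50:42, 0.5% at 52:40, 98% at 55:37 and about 100% at 61:31.
- 230 specimens: rejects 0.1% at 125:105, 99.9% at 130:100 and about 100% at 153:77.

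A perfect assay rejects 0% at each of these ratios.

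**5. Other readings of PPV.**
- *Within each group, as literally worded.* Every CC specimen comes from a patient already known to have CC, so the PPV within that group is 100% by design; the same holds for UC.
- *P(CC | DEFA5+) and P(UC | DEFA5+).* In a CC/UC sample these sum to 100%; 80% + 77% = 157%.
- *DEFA5-positive share of each group.* Comparing these shares does address separation, but they are not PPVs, and 80% against 77% contradicts the stated 19.

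**The case against.** The strongest reply is that the author meant the DEFA5-positive share in each group. The test would then be a reasonable, if weak, check of separation, and the fault would be a wrong label and a wrong number. This cannot be excluded. Nor can the reading be dismissed because 80% and 77% are close, since the same sentence states 19 points and at least one figure must be wrong. But the text says PPV and describes the probability of truly having the disease given a positive test. On either reading the sentence needs correction.

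Three stronger conclusions are tempting, and the Protocol does not support them.
- A reader might infer that any excess of CC specimens lets a worthless marker through. It does not: about 1.5:1 is needed at 92 specimens and about 1.3:1 at 230. The Protocol suggests no such imbalance.
- A reader might infer that "Sampling Method: Probability Sample" contradicts the known-diagnosis groups and fixed arms. Random sampling within diagnosis strata of a repository, with fixed stratum sizes, is a probability sample, so no contradiction is shown.
- A reader might treat the test as the study's success criterion. The Protocol gives it only as a sample-size justification, and the secondary outcome may be analysed otherwise in a SAP that is not at hand.

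It is also fair to say that some accurate but unbalanced assays, such as 90%/99%, often reject. That confirms that the contrast responds to imbalance.

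**Conclusion.** The point holds for the sample-size justification of the known CC and UC arms. As worded, the 230 rests on a contrast that rejects in 0% of trials for a perfect assay, 3–4% for a 95%/95% assay and 93–100% for a 60%/95% assay. These rates assume the call-based PPV reading, the CC-greater tail, a pooled z-test and equal arms of 46 to 115. The algebra behind them needs only the PPV reading. If positive shares were meant, the finding reduces to a mislabelled quantity with inconsistent figures, which still leaves the 230 unsupported as written. The point does not reach the primary outcome (choice of antibody), the IC group or analyses that a SAP may contain.

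**What to change.** In Eligibility, Study Population, replace the PPV-difference justification with sensitivity in known CC and specificity in known UC, each reported with a 95% CI against a minimum that the sponsor states. A weaker option is to test P(DEFA5+ | CC) > P(DEFA5+ | UC), which shows only better-than-chance separation. State the CC and UC arm sizes and the power that those planned sizes give. Report PPV and NPV only as derived values at stated CC prevalences.

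Illustration, with an assumed 80% minimum, an exact one-sided 5% test per arm and both required to pass (joint power is the product of two independent arms):
- 46 per arm, at least 42 correct: 0.921² = 85% if both true values are 95%; 0.507² = 26% if both are 90%.
- 115 per arm, at least 100 correct: 0.890² = 79% if both are 90%.

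The cost is a rewritten sample-size statement, power that may look less favourable than the stated 80%, and a PPV headline that depends on prevalence. The fix itself requires no added specimens; whether the restated power is enough is for the sponsor to decide.

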ClinicalTrials.gov PRS **DRAFT Receipt (Working Version)**

Last Update: 11/15/2022 20:55

ClinicalTrials.gov ID: [Not yet assigned]

Study Identification

Unique Protocol ID: 22-08-1235

Brief Title: Evaluate Established Anti-DEFA5 mAbs Diagnostic Efficacy and Safety in IBD

Official Title: Evaluate Established Anti-DEFA5 mAbs Diagnostic Efficacy and Safety in IBD

Secondary IDs:

Study Status

Record Verification: November 2022

Overall Status: Not yet recruiting

Study Start: June 1, 2023 [Anticipated]

Primary Completion: May 31, 2025 [Anticipated]

Study Completion: June 30, 2025 [Anticipated]

Sponsor/Collaborators

Sponsor: Meharry Medical College

Responsible Party: Principal Investigator
Investigator: [name] [[name]]
Official Title: Professor
Affiliation: Meharry Medical College

Collaborators:

Oversight

U.S. FDA-regulated Drug:

U.S. FDA-regulated Device:

U.S. FDA IND/IDE:

Human Subjects Review: Board Status: Exempt

Data Monitoring: Yes

Study Description

Brief Summary: Investigators propose to validate efficacy and safety of the detection of DEFA5 in the diagnosis of the colonic IBD using longitudinal vs. cross-sectional studies of known patient clinical data to correlate with their endoscopy biopsy data. 30% of colonic IBD patients cannot be accurately diagnosed (CC vs. UC) in a timely manner even when a state-of-the-art classification system of combined clinical, endoscopic, radiologic and histologic tools is used. When the diagnostic classification for these two diseases is inconclusive, the condition is termed indeterminate colitis (IC). Here, the central medical challenge is the discrimination of IBD into the specific subtypes with high accuracy, as it greatly affects surgical care of patients. Diagnostic accuracy of IC into either authentic UC or CC is of utmost importance when determining a patient's candidacy for

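### The one-tailed 5% comparison of the CC and UC PPVs has no stated alternative or rationale and, as written, cannot declare the CC value lower than the UC value

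*Protocol*

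**What the plan says.** The Protocol names one inferential test, in Eligibility under Study Population. The comparison is made "using a one-tailed test of proportions between the two groups with 80% statistical power and a 5% level of significance". The total of 230 is presented as enough for a 19-point gap, and the rates attached to that gap are "80% probability that subjects in the CC group with a positive screening test truly have the disease and 77% PPV for subjects in UC group". No sentence gives the alternative hypothesis or explains why only one direction is of interest. The direction has to be read from CC being printed as the larger value.

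The sizes of the CC and UC groups are not stated. The same paragraph gives 46 for each of two non-IBD arms, and Study Design lists five groups and an enrollment of 230.

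On what is at stake, the Brief Summary says "Diagnostic accuracy of IC into either authentic UC or CC is of utmost importance" when candidacy for RPC-IPAA is decided, and describes that operation as the standard curative procedure for UC. The Detailed Description adds: "Incorrect diagnosis and surgery carry potential morbidity from inappropriate and unnecessary surgery and cost".

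**The concern.** A one-tailed test suits a question in which a result in the other direction would be read in the same way as no difference. The Protocol does not argue that here, and its aims point the other way. The assay's premise is that DEFA5 marks CC. If CC's PPV proved clearly lower than UC's, that would be an important adverse finding about the assay, and a test of CC above UC has no rejection region for it. The PPVs could still be estimated and reported, but the named test could only fail to reject.

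The 80% power is also quoted at a one-sided 5% level, which has the same critical value as a two-sided 10% test. A reader used to two-sided 5% designs would take the comparison to be stronger than it is.

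**Working it through.** **Inputs from the Protocol.** One-tailed test, alpha 0.05, power 0.80, N = 230, difference 19 points, rates 80% (CC) and 77% (UC), arms of 46 for the two non-IBD groups, five groups, and an earlier PPV of 96% in the Brief Summary.

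**Assumptions.** Each group's size serves as the denominator of its proportion. CC and UC have either 46 each (5 × 46 = 230) or 115 each (230 / 2). A 19-point gap is either 96% vs 77%, since 96% is the only printed figure 19 points above 77%, or 80% vs 61%.

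**Formula.** Pooled z test with n per group:
- p̄ = (p1 + p2)/2
- SE0 = √[2p̄(1 − p̄)/n]
- SE1 = √{[p1(1 − p1) + p2(1 − p2)]/n}
- power = Φ[(p1 − p2 − z·SE0)/SE1], with z = 1.645 one-tailed and 1.960 two-sided.

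**Reproducing the stated figure.** The printed rates differ by 80 − 77 = 3 points, not 19. They would need 2,318 per group one-tailed (4,636 in total). At 46 and 115 per group the one-tailed power is 9.8% and 13.7%. With a 19-point gap and equal groups, CC plus UC need 78 in total (96% vs 77%) or 142 (80% vs 61%), not 230. The nearest reconstruction is 96% vs 77% with 46 per group, where a one-sided Fisher test has 81.3% power. So the stated figure is approached only under assumptions the Protocol does not state.

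**Worked example, 46 per group, 96% vs 77%.** p̄ = 0.865, SE0 = 0.07125, SE1 = 0.06845.
- One-tailed: (0.19 − 1.645 × 0.07125)/0.06845 = 1.064, power 85.6%.
- Two-sided: (0.19 − 1.960 × 0.07125)/0.06845 = 0.736, power 76.9%.

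**Power, one-tailed against two-sided at 5% (pooled z approximation).**

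| Per group | Rates | One-tailed | Two-sided | Loss (points) |
|---|---|---|---|---|
| 46 | 96% vs 77% | 85.6% | 76.9% | 8.7 |
| 46 | 80% vs 61% | 64.1% | 51.6% | 12.5 |
| 115 | 80% vs 61% | 93.9% | 89.0% | 4.9 |
| 115 | 96% vs 77% | 99.6% | 99.1% | 0.5 |

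**Sensitivity to method, first row.** Exact binomial enumeration of the same pooled z test gives 88.9% one-tailed and 82.5% two-sided. Fisher's test gives 81.3% and 71.7%. Whether the two-sided figure lies above or below 80% therefore depends on which test is meant.

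**Gap reversed (CC lower by 19 points), test of CC above UC, exact enumeration of the pooled z test.**

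| Per group | CC vs UC | One-tailed rejects | Two-sided rejects |
|---|---|---|---|
| 46 | 77% vs 96% | about 0.0006% | 82.5% |
| 46 | 61% vs 80% | about 0.012% | 52% |
| 115 | 61% vs 80% | below 0.0001% | 89% |
| 115 | 77% vs 96% | below 0.0001% | 99.5% |

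**The case against.** The strongest reply is that the direction is not arbitrary. The Protocol describes a mechanism in which DEFA5 identifies tissue consistent with CC, and it prints CC above UC. If the comparison were DEFA5 positivity in CC against UC, a reversed result would simply mean the assay had failed, and one tail could be defended. That stands for positivity. The comparison actually written is of two PPVs, for which the mechanism does not fix which is higher, and no reason of this kind is given.

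A second reply is that sidedness does not protect against wrong calls. This stands too. The test asks whether two PPVs differ; if both were equally poor, neither version would show it. A two-sided test shows which PPV is lower and no more.

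Third, a reader might infer that the Protocol names two harmful wrong calls, one in each direction, and that the test ignores one of them. It does not. It calls incorrect diagnosis harmful in general and gives surgical candidacy as the example. Splitting this into two errors is an inference from a two-class call.

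Fourth, the 3-point versus 19-point contradiction is the larger defect in the same paragraph. At the printed rates, power is 9.8% to 13.7% one-tailed and 5.4% to 8.0% two-sided at 46 to 115 per group. That is correct, but repairing the rates would leave the unexplained tail in place.

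**Conclusion.** The point holds in a limited form. The only inferential test named in this document is one-tailed at 5%, with its direction implied rather than stated and no rationale. It cannot declare CC's PPV lower than UC's, although accuracy into either disease is said to matter. For a reversed 19-point gap the chance of rejection is at most about 0.012%, against 52% to 99.5% two-sided. That contrast holds in all four scenarios, although the rates and group sizes in them are assumptions.

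It is tempting to add that the stated 80% power exists only because of the single tail. The documents do not support that. Under the nearest reconstruction the two-sided power is 71.7%, 76.9% or 82.5% depending on the test and method, and with 115 per group it stays at 89.0% or above. Nor can this be called the only planned test, since a statistical analysis plan may exist. The comparison is also not tied to the listed primary outcome, which is assessment of the two antibodies. The change is worth making because it is cheap and the study had not begun recruiting.

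**What to change.** In Eligibility, Study Population, replace the one-tailed 5% test with a two-sided 5% test for the CC-versus-UC PPV comparison. Alternatively, keep one side at 2.5% and state the direction and the reason for it.

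In the same edit, reconcile the 19-point difference with the printed 80% and 77%, state the CC and UC group sizes, and name the test (pooled z or Fisher). Then restate the power at the existing specimen numbers; a figure given before those corrections would mean little.

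The sidedness change is one sentence and needs no additional specimens. Its cost is lower stated power: 0.5 to 12.5 points by the pooled z approximation across the four scenarios. Because a two-sided test would still miss two equally poor PPVs, it should not be presented as a safeguard against misdiagnosis.

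### The sample-size statement applies a two-group test of proportions to PPVs, but the CC and UC groups are fixed by diagnosis and are not the PPV denominators, so the stated 5% level and 80% power do not follow from that test

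*Protocol*

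**What the plan says.** The Protocol's only sample-size statement is in Eligibility, Study Population. It takes 230 subjects as enough to detect "a clinically significant difference of 19% between the PPVs of CC and UC". The comparison is to be made "using a one-tailed test of proportions between the two groups with 80% statistical power and a 5% level of significance". It explains the CC figure as "80% probability that subjects in the CC group with a positive screening test truly have the disease" and gives 77% for UC. The quantity compared is thus a proportion among subjects with a positive test.

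Groups and Interventions defines the two groups by diagnosis. For the Crohn's colitis cohort: "Investigators will determine DEFA5 levels from endoscopy biopsies from known authentic CC patients". For the ulcerative colitis cohort: "Investigators will determine DEFA5 levels from endoscopy biopsies from known authentic UC patients". The secondary outcome likewise refers to patients whose diagnosis is already known.

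The Protocol gives no size for the CC or UC group, no CC:UC mix and no expected number of CC or UC calls. Study Design labels the study cross-sectional, and Eligibility labels the sampling a probability sample.

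**The concern.** A two-group test of proportions treats each denominator as a fixed number of independent subjects. If the groups are known CC and known UC patients, they cannot be the denominators of the two PPVs. Within a group of authentic CC patients, everyone who tests positive has CC, so the PPV there is 100% by construction.

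The denominators have to be the patients called CC and the patients called UC. Those counts are random, and they are linked. A CC patient who is misclassified leaves the numerator of the CC PPV and enters the denominator of the UC PPV. The two estimates are then positively correlated, and the binomial standard error of their difference does not apply.

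This is the only hypothesis test named in the record and the sole basis given for 230. If its level and power are not what the text states, the sample-size justification does not support the design.

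**Working it through.** **Inputs from the Protocol.** One-tailed level 5% (critical value 1.645); power 80%; difference 19 points; PPVs 80% and 77%; total 230; five cohorts; 46 + 46 = 92 non-IBD samples.

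**Assumptions, because the Protocol gives no figure.** Every CC and UC sample receives a CC or UC call; the groups are equal, n each, with n = 46 (230/5), 69 ((230 − 92)/2) or 115 (230/2); the target population has the same 50:50 mix. Pairs examined: the printed 80/77, and two pairs that are 19 points apart, 80/61 and 96/77 (96% is the PPV that the Brief Summary reports from colectomy specimens).

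**Step 1: the plan's own figure.** With the ordinary two-sample formula, one-tailed:
- 80/77 needs 2,318 per group.
- 80/61 needs 71 per group with the pooled variance. Unpooled, it needs (1.645 + 0.842)² × (0.80×0.20 + 0.61×0.39) / 0.19² = 68.1, so 69.
- 96/77 needs 39 per group.

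None of these gives 230 for a two-group comparison. The nearest route is 2 × 69 + 92 = 230. It replaces the printed 77% with 61% and counts the added non-IBD samples inside 230.

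**Step 2: variance with the groups fixed.** Let a be the CC patients called CC, and d the UC patients called UC. Then a ~ Bin(n, Se) and d ~ Bin(n, Sp), independently, with
- PPV_CC = a / (a + n − d)
- PPV_UC = d / (d + n − a)

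With equal groups, both PPVs equal s exactly when Se = Sp = s. The derivative of PPV_CC − PPV_UC is then (1 − s) − s = 1 − 2s with respect to a/n, and s − (1 − s) = 2s − 1 with respect to d/n. So
- true variance ≈ (2s − 1)² × 2s(1 − s)/n
- planned variance ≈ 2s(1 − s)/n

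At s = 0.80 the ratio is 0.6² = 0.36. With n = 46 the planned SE is √(2×0.80×0.20/46) = 8.3 points. Exact enumeration gives a true SD of 5.1.

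**Step 3: actual level.** Exact enumeration over a and d, pooled z-test, rejecting above 1.645:

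| Common PPV | 46 per group | 69 | 115 |
|---|---|---|---|
| 77% | 0.2% | 0.2% | 0.2% |
| 80% | 0.4% | 0.4% | 0.4% |
| 86.5% | 1.3% | 1.4% | 1.3% |
| 90% | about 2% | about 2% | about 2% |

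The level nears 5% only as the PPV nears 1 (4.6% at 96%, 46 per group). More patients do not remove the error, because the variance ratio does not depend on n.

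**Step 4: actual power of the stated test.** Se and Sp follow from the PPVs. For 80/61 the share of CC calls is (0.50 − 0.39)/(0.80 − 0.39) = 0.268, so Se = 0.268×0.80/0.50 = 0.429 and Sp = 0.732×0.61/0.50 = 0.893. In the same way 96/77 gives 0.710 and 0.970, and 80/77 gives 0.758 and 0.811.

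| Pair | 46 per group | 69 | 115 |
|---|---|---|---|
| 80 vs 77 | 1.3% | 2.0% | 3.1% |
| 80 vs 61 | 55% | 82% | 99% |
| 96 vs 77 | 92% | 99% | >99.9% |

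At 46 per group the textbook calculation gives 9.8%, 64% and 86% for these pairs. A delta-method SE that holds the groups fixed gives 15.6%, 98% and 99%.

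**Step 5: sample mix different from the target mix.** With 69 per group and PPVs truly equal (77% to 86.5%) in a population with another CC share, the stated test rejects 11–12% of the time at a share of 45%, 46–66% at 40%, and below 0.1% at 55%.

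**The case against.** **The design labels.** If diagnosis were left random, as in a true cross-sectional probability sample, the stated test would hold its level: simulation gives about 5.0–5.2%. But cohorts made up of known CC and known UC patients are not such a sample, so the labels do not rescue the level.

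**The 80/77 mismatch comes first.** The printed PPVs differ by 3 points, not 19, and that alone breaks the stated power. This is true, and it is a separate error. Correcting those numbers would leave the wrong variance in place.

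**The variance method belongs in the SAP.** The choice of variance for the final analysis may well be specified there, and the SAP is not at hand. What can be criticised is narrower: the Protocol names a test and attributes a level and a power to it, and these do not follow.

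**The figures rest on assumptions.** This stands. Group sizes, equal allocation, the forced two-way call and the target mix are not in the Protocol. The level at a given PPV hardly changes with group size, but it changes greatly with the mix (Step 5).

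**Stronger readings to avoid.** A reader might infer that the study is underpowered because of this error. The calculations do not support that in general: the stated test has 82% power for 80/61 at 69 per group, and for 96/77 at 46 per group it exceeds the textbook figure (92% against 86%). Part of the 55% for 80/61 at 46 per group reflects the assumed group size, since the textbook power there is only 64%. A reader might also infer that the test is always too strict. That holds for equal groups matching the target mix, not when the mix differs.

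**Conclusion.** The point holds as a defect of the sample-size statement. The CC and UC groups, fixed by diagnosis, cannot be the denominators of the two PPVs, so the stated 5% level does not follow from the stated test and the stated 80% power cannot be derived from it.

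Under a two-way call and equal groups matching the target mix, the actual level is roughly a twelfth of the stated one at a PPV of 80% (0.4% against 5%). Power runs from 1–3% for the printed pair to above 99%, depending on the PPV pair and group size. The principle rests on the Protocol's text and is firm. The individual figures are illustrations under the listed assumptions. The documents do not show that power is lost overall, nor that the eventual analysis will use this variance.

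**What to change.** In the Study Population text, choose one of two routes.

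(a) Keep the PPV contrast. State the CC and UC group sizes and the assumed CC:UC mix, and use a variance that holds the diagnosis groups fixed: a bootstrap or exact calculation stratified by diagnosis, or the delta method. If the delta method is used, check its actual level at the planned sizes. It gives 5.1–6.1% with 46 per group at PPVs of 77–90%, but 9.3% (PPV 80%) and 10.6% (PPV 90%) with 30 CC and 62 UC.

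(b) Redefine the comparison as sensitivity and specificity within the diagnosis groups, where the group sizes really are the denominators. This is a different hypothesis and needs its own margin and direction. With equal groups, a higher CC PPV means Se below Sp, so the tail reverses. A 19-point PPV gap becomes 26 points for 96/77 (0.970 − 0.710) or 46 points for 80/61 (0.893 − 0.429). With unequal groups the null also differs: at 40 CC and 52 UC with both PPVs at 80%, the test on these shares in the reversed direction rejects 55% of the time.

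Either way, restate the level and power from that calculation, and reconcile the 80/77 and 19-point figures at the same time. The cost is a little analysis work and a changed power figure, with no extra patients or assays.
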